Study design:	Prospective, observational, pilot study
Study participants:	Patients with pacemakers for bradycardia.
Planned sample size:	150 participants.
Follow up duration:	Not applicable.
Planned study period:	July 2025-June 2026
Aims:	To determine whether new technologies can improve the detection of pacemaker-associated heart failure.

FUNDING

Leeds Hospitals Charity: Research and Innovation Funding.

ROLE OF STUDY SPONSOR AND FUNDER

The University, when acting as Sponsor assumes overall responsibility for the initiation and management of the study.

Neither Sponsor or the Funder have any role in the study design, data analysis and interpretation, manuscript writing, conduct, and dissemination of results, nor have final decision regarding any of these aspects of the study.

STUDY PROTOCOL

OPTimising a screening program to detect pacemaker-associated heart failure using Artificial Intelligence (OPT-AI)

1. BACKGROUND

1.1 PACEMAKERS FOR THE TREATMENT OF BRADYCARDIA

Permanent pacemaker implantation for the treatment of bradycardia (slow heart rates) improves quality of life and normalises life expectancy.^{1,2} Around 600,000 people undergo implantation of a pacemaker device each year, and there are around 3 million people currently living with pacemakers worldwide. Typical pacemaker devices for bradycardia consist of a generator implanted into a pre-pectoral pocket, with a lead in the right ventricular (RV) apex, with or without a second lead in the right atrial appendage. Usually, battery life is around 8-12 years, after which time a generator replacement is required.

1.2 RIGHT VENTRICULAR PACING AND HEART FAILURE

Although pacemakers can transform a patient's quality of life, there are some disadvantages. Compared with intrinsic electrical conduction, RV apical electrical stimulation results in electrical and mechanical dyssynchrony, leading to acute changes in LV performance, and over the long-term adverse left ventricular (LV) remodelling, progressive systolic dysfunction and, in some, the clinical syndrome of heart failure. Patients with pacemakers for bradycardia often have co-morbidities, such as ischaemic heart disease or hypertension which can make this problem more likely. Pacemaker-associated heart failure is the most common long-term complication of device implantation, however this is often unrecognised, and although certain patient characteristics make it more likely, it is not currently possible to identify individuals who might develop heart failure in the future.³

1.3 ALTERNATIVE STRATEGIES TO PREVENT HEART FAILURE

The burden of RV apical pacing is positively correlated with the risk of HF hospitalisation. RV pacing avoidance algorithms can reduce this burden,⁴ however, this is often unavoidable for patients with high-degree atrioventricular (AV) block.⁵ Alternative strategies such as the implantation of devices capable of delivering biventricular pacing (cardiac resynchronisation therapy), septal or conduction system pacing are available. However, each had its own limitations including longer procedure times, premature lead failure, financial costs, the higher risk of upfront complications, and more fundamentally, that none of these strategies have not been proven to improve clinical outcomes.⁶ The RV apical position continues to be far and away the most common site for ventricular lead implantation for patients implanted with pacemakers for bradycardia.

1.4 THE PACEMAKER CARE PATHWAY AND THE OPPORTUNITY TO INTERVENE

The implant procedure itself is only one aspect of the pacemaker pathway of care. Following implantation patients are required to have ongoing follow-up to assess device functionality and battery longevity. Standard practice is for patients to attend a clinic in person, even for those who now benefit from the provision of remote monitoring. Additionally, towards the end of a device's lifespan, patients are required to undergo a day case procedure to undergo generator replacement. Both of these offer the opportunity to assess for pacemaker-associated heart failure during a patient's routine hospital contact.

1.5 THE ROLE OF CARDIAC ULTRASOUND IN DIAGNOSIS AND CLASSIFYING HEART FAILURE

Cardiac ultrasound, or echocardiography, is fundamental to the diagnosis and management of heart failure. A diagnosis of heart failure requires assessment of cardiac structure and function, and although alternative imaging modalities are available, cardiac ultrasound is almost always the initial imaging modality used to make the diagnosis. Furthermore, heart failure is currently classified by left ventricular ejection fraction (LVEF) into heart failure with

reduced (HFrEF) or preserved ejection fraction (HFpEF). Optimal care for people with HFrEF now includes four classes of medications proven to reduce hospitalisation and mortality risk.⁷ Each of these pharmacological therapies result in incremental benefits to patients, and guidelines now recommend these are initiated in parallel, as soon as possible following the discovery of heart failure.⁸ This is unlike the situation in HFpEF, where these therapies have either proven neutral, or have resulted in marginal improvements to outcomes. An assessment of LVEF with echocardiography is therefore essential. Until recently the effect of these agents for pacemaker-associated heart failure was unknown, and most phase III clinical trials of medical therapy for HFrEF did not report the effect of these agents for patients with pacemakers. Additional strategies to improve outcomes include device 'upgrade' procedures, in which an additional LV lead is implanted to deliver biventricular pacing (cardiac resynchronisation therapy), with or without a defibrillator.

2. PILOT DATA

2.1 RIGHT VENTRICULAR PACING RESULTS IN IMMEDIATE ADVERSE EFFECTS ON LEFT VENTRICULAR FUNCTION, AND ADVERSE REMODELLING IN THE LONG-TERM

We performed a single-centre, observational study of patients previously implanted with pacemakers for bradycardia and used cardiac magnetic resonance (CMR) imaging to determine the immediate effects of RV pacing on LV systolic function. We recruited 84 patients with an LVEF $\geq 40\%$ into two observational studies. In 34 patients with preserved atrio-ventricular conduction, we programmed two pacing modes to deliver asynchronous atrial pacing (with intrinsic conduction) or asynchronous dual chamber pacing (forced RV apical pacing) during CMR. In a second study, patients with high degree AV block underwent a CMR at baseline and then again after 6-months

2.2 SCREENING FOR AND TREATING HEART FAILURE IN PATIENTS WITH PACEMAKERS IMPROVES OUTCOMES

OPT-PACE (OPTimising PACEmaker therapy) was a multi-centre, randomised controlled trial enrolling people with pacemakers implanted for bradycardia. Participants were randomised 1:1 to echocardiography screening or usual care. For participants in the screening arm found to have LVSD (LVEF $< 50\%$), we then compared patients managed by their primary care physician with those managed in a combined heart failure and devices clinic. The primary outcome was the time to death or first hospitalisation due to heart failure. We randomized 1201 participants were randomised, 600 to echocardiography screening and 601 to usual care. Patients in the echocardiography screening arm who were managed within a combined heart failure and devices clinic had better optimisation of medical therapy for heart failure and were at around a third lower risk of the combined primary endpoint (hazard ratio 0.67 [0.46-0.98]).

2.3 SUMMARY AND LIMITATIONS OF THE AVAILABLE EVIDENCE

Pacemaker-associated heart failure with the most common long-term complication of pacemaker implantation. We now have robust evidence that show that echocardiography screening identifies heart failure in one third of patients attending routine pacemaker follow up, and that where this is identified and then treated clinical outcomes are improved. However, this approach has limitations. First, an echocardiogram takes approximately 45 minutes to perform, analyse and report. Second, the technicians running the pacemaker clinics are not usually skilled in echocardiography. Third, each scan costs around £120, or approximately £540,000 to assess all 4,500 patients currently under the care of Leeds Teaching Hospitals Trust. A new approach is needed.

3. HYPOTHESIS

[figure not shown]

Figure: Screening for heart failure reduces the risk of all-cause mortality or heart failure hospitalization (Paton et al. *Nat Med.* 2024)

Artificial intelligence (AI) can detect pacemaker-associated heart failure with similar levels of accuracy compared to echocardiography.

4. RESEARCH QUESTION

4.1 PRIMARY RESEARCH AIM

To determine the accuracy of AI derived LVEF compared to standard cart-based echocardiography with left ventricular ejection fraction (LVEF - the percentage of blood pumped during each heart beat) measured by biplane method, assessed by correlation coefficient.

4.2 SECONDARY RESEARCH AIMS

To determine the accuracy of AI determined abnormal left ventricular ejection fraction (LVEF <50%) compared to standard cart-based echocardiography measurement of LVEF <50% by biplane method, determined by sensitivity, specificity, positive and negative predictive values. To determine the incremental improvement of a model to predict LVEF <50% in a population with pacemakers of the addition of AI derived LVEF, point of care NT-proBNP, or both.

To determine the proportion of participants in whom it was not possible to determine AI derived LVEF, LVEF measured by biplane method, or subjective visual estimation of LVEF.

5. STUDY SETTING

We will recruit potential participants from those attending routine pacemaker clinic follow-up at the Leeds Teaching Hospitals NHS Trust. All study procedures will be undertaken at the Leeds National Institute for Health and Care Research Cardiovascular Clinical Research Facility (CRF). The Leeds Cardiovascular CRF has facilities and equipment available for echocardiography and pacemaker interrogation, as well as appropriately trained staff to conduct the study procedures.

6 IDENTIFICATION OF POTENTIAL PARTICIPANTS

6.1 ELIGIBILITY CRITERIA

We require patients to have standard pacemakers implanted for the management of bradycardia, and for at least 20% of heart beats to be paced (right ventricular pacing burden >20%) as these patients are at risk of developing pacemaker-associated heart failure. Patients with specialised types of pacemakers which reduce the risk of developing heart failure (conduction system pacemakers) or have been implanted for the management of known heart failure (cardiac resynchronisation therapy pacemakers/defibrillators, implantable cardioverter defibrillators) are not eligible for inclusion.

6.2 INCLUSION CRITERIA

Adult patients aged ≥ 18 years.

Patients with existing pacemakers who have a RV pacing burden $\geq 20\%$.

Ability to provide informed consent.

6.3 EXCLUSION CRITERIA

Patients who are unwilling or unable to provide informed consent.

Patients known to have heart failure

Patients with any previous measurement of LVEF <50%.

Patients with conduction system pacemakers.

Patients with cardiac resynchronisation therapy pacemakers/defibrillators.

Patients with implantable cardioverter defibrillators.

Patients with leadless pacemakers.

7 RECRUITMENT PROCESS

7.1 PARTICIPANT IDENTIFICATION

To make participation as simple as possible, and to avoid unnecessary visits to the hospital, patients will be approached prior to their routine pacemaker clinic appointment. Patients who

have pacemakers attend the hospital every 6-12 months in person to undergo a check of their pacemaker's battery life and functionality. All potential participants will be identified by a member of the patient's direct care team according to the study inclusion criteria. Potential participants will be sent an Invitation Letter and the Patient Information Sheet, offering them the opportunity to attend an appointment in the Leeds Cardiovascular Clinical Research Facility instead of their usual pacemaker clinic appointment. This will then be followed up by a telephone call from the direct care team, and only those who are potentially interested and confirm their agreement to have their information passed to the research team will be approached to arrange an appointment.

7.2 CONSENT PROCESS

The Chief Investigator retains overall responsibility for the conduct of research at this site, this includes the receiving of informed consent of participants at the site. They must ensure that any person delegated responsibility to participate in the informed consent process is duly authorised, trained and competent to participate according to the ethically approved protocol, principles of Good Clinical Practice (GCP) and Declaration of Helsinki.

On the day of the appointment, a member of the research team will approach the patient, explain the study and offer the opportunity to ask questions. Participants will have already had at least one week to read the Participant Information Sheet and to consider whether they wish to take part. If willing to participate, they will then provide written consent to undertake the study procedures. All patients, regardless of whether they consent to participate in the research study, or not, will have a pacemaker safety check completed as part of their usual clinical care by an accredited cardiac physiologist.

8. EXPERIMENTAL DESIGN

A single centre, prospective, observational study enrolling patients with existing pacemakers.

9. STUDY PROCEDURES

9.1 BASELINE STUDY PROCEDURES

Participants will attend an appointment at the Leeds Cardiovascular Research Facility. They will have already received the Participant Information Sheet at least a week prior to their appointment, if willing to participate they will provide informed written consent. We will then collect demographic and clinical data from the participant's electronic healthcare record prior to undergoing the study procedures. Participants will undergo a routine device interrogation by an accredited cardiac physiologist as per usual clinical care to confirm device functionality and RV pacing burden $\geq 20\%$. Participants will undergo point-of-care blood testing for NTpro-BNP, a hand-held echocardiogram and a standard cart-based echocardiogram. The appointment is expected to last around one hour. Following the appointment a member of the research team will arrange their next scheduled pacemaker clinic appointment with their usual care team.

9.2 POINT OF CARE NTPRO-BNP BLOOD TESTING

LumiraDx (LumiraDx Ltd, Cayman Islands) is a quantitative point-of-care, fingerpick blood test capable of measuring various biomarkers using a micro-sample of blood obtained from a finger prick. The LumiraDx can measure NTpro-BNP with only $20\mu\text{L}$ of blood, is highly portable, with a turn-around time of only 12 minutes – feasible within the time constraints of a standard pacemaker follow-up appointment. Their technology has been validated in a study of 659 samples compared to gold-standard commercially available laboratory equipment (Roche Cobas Elecsys proBNP II assay) and found to have comparable accuracy (slope 0.86, intercept -4.12, $r = 0.97$).

9.3 STANDARD CART-BASED CARDIAC ULTRASOUND

Participants will undergo a transthoracic echocardiogram by a senior cardiac physiologist accredited by the British Society of Echocardiography (or equivalent international body) using

a GE Healthcare Vivid E95 Ultra Edition Cardiac Ultrasound. A minimum dataset will be obtained with LVEF measured by the biplane method where possible, as well as assess for any (at least) moderate valvular disease or other finding which could result in a change to patient management.

9.3 HAND-HELD CARDIAC ULTRASOUND USING ARTIFICIAL INTELLIGENCE

Participants will undergo a focussed hand-held echocardiogram with AI derived LVEF using the Kosmos platform (EchoNous Inc., Redmond, USA) a point-of-care, hand-held ultrasound device capable of cardiac imaging, which uses US2.AI (Ultrasound Anyone Anywhere, Singapore) integrated AI driven software capable of automated measurement of LVEF. Existing data suggest the Kosmos platform is able to reliably detect abnormal LVEF in patients referred with suspected heart failure, however there are no data describing its use in a population with pacing-induced LV dysfunction. Hand-held echocardiography will be done by a specialist nurse or cardiac physiologist who does not hold accreditation in echocardiography.

10 OUTCOMES

10.1 PRIMARY OUTCOME

The accuracy of AI derived LVEF compared to standard cart-based echocardiography with LVEF measured by biplane method, assessed by correlation coefficient.

10.2 SECONDARY OUTCOMES

- The accuracy of AI derived LVEF <50% compared to standard cart-based echocardiography measurement of LVEF <50% by biplane method, determined by sensitivity, specificity, positive and negative predictive values.
- The incremental improvement of a model to predict LVEF <50% in a population with pacemakers of the addition of AI derived LVEF, point of care NT-proBNP, or both.
- The proportion of participants in whom it was not possible to determine AI derived LVEF, LVEF measured by biplane method, and subjective measurement of LVEF.

10.3 SAFETY OUTCOMES

- The proportion of patients with a new diagnosis of at least moderate valve disease, or any other echocardiography finding which resulted in a change to patient care.

11. STATISTICAL ANALYSIS

11.1 POWER CALCULATIONS

For this pilot study all analyses are exploratory, no statistical hypothesis has been prespecified and no formal sample size calculation has been performed. Based on previously published work assessing the accuracy of AI derived LVEF and sonographer determined LVEF we anticipate the inclusion of 150 participants would provide adequate statistical power to compare the two imaging modalities.

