11.2 PRIMARY OUTCOME

The comparison of AI derived LVEF and sonographer measured LVEF will be determined by correlation coefficient.

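### Does the remark in Protocol section 11.1 that 150 participants give adequate power, made beside a disclaimer of any calculation, require a change?

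*Protocol*

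**What the plan says.** Protocol section 11.1 makes two statements in succession. The first calls the study a pilot with exploratory analyses and says that "no statistical hypothesis has been prespecified and no formal sample size calculation has been performed". The second appeals to earlier published work, with no reference number or figure, and says that "we anticipate the inclusion of 150 participants would provide adequate statistical power to compare the two imaging modalities".

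The related text is brief. Section 3 gives a general hypothesis that AI "can detect pacemaker-associated heart failure with similar levels of accuracy compared to echocardiography", without a margin. Section 11.2 gives the primary analysis: "The comparison of AI derived LVEF and sonographer measured LVEF will be determined by correlation coefficient". Sections 4.1, 10.1 and 11.2 state no null value, target correlation, error rate or power level. Section 10.2 foresees some unusable measurements, since one outcome is "The proportion of participants in whom it was not possible to determine AI derived LVEF", but no rate is assumed.

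**The concern.** The two sentences of section 11.1 sit badly together. Power is the probability of rejecting a stated null, under a stated alternative, at a stated error rate. A plan that sets no hypothesis and runs no calculation has no defined power, so calling it adequate can be neither confirmed nor refuted.

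The sentence is also the only reason given for the number 150. Section 3 speaks of similar accuracy and the primary measure is a correlation. A reader might therefore take a correlation clearly above zero as adequately powered evidence that the two methods agree, which the design does not provide.

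**Working it through.** **Inputs from the protocol.** N = 150 (section 11.1). Primary measure: a correlation coefficient (section 11.2). Null, target, error rate, power level and expected loss of pairs: not stated. The only yield figure is in section 2.3: "echocardiography screening identifies heart failure in one third of patients attending routine pacemaker follow up".

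**Reproducing the plan's figure.** There is no power figure to reproduce. What can be checked is how far power depends on the missing hypothesis.

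**Power at 150 pairs.** Assumptions: Fisher z, two-sided 5%, all 150 pairs usable.

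Power = Φ(|atanh r1 − atanh r0| × √(n − 3) − 1.96), with √147 = 12.124.

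Worked example, 0.80 against 0.70: atanh values 1.0986 and 0.8673, difference 0.2313. Then 0.2313 × 12.124 = 2.804, less 1.96 gives 0.844, and Φ = 0.80.

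| True r (assumed) | Null r (assumed) | Power at 150 | N for 80% power |
|---|---|---|---|
| 0.50 | 0 | above 99.99% | 30 |
| 0.30 | 0 | 96% | 85 |
| 0.80 | 0.70 | 80% | 150 |
| 0.70 | 0.60 | 56% | 262 |
| 0.85 | 0.80 | 48% | 320 |
| 0.80 | 0.75 | 33% | 501 |

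N for 80% power = ((1.96 + 0.8416) / (atanh r1 − atanh r0))² + 3, rounded up.

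These rows are illustrations, not bounds; other pairs would give other values. One row returns exactly 150, but the protocol says no formal calculation was made, so the match is no evidence of how the number arose.

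**Precision of the primary measure.** The 95% interval is tanh(atanh r ± 1.96/√(n − 3)). For r = 0.80 and n = 150: 1.0986 ± 0.1617, giving 0.73 to 0.85. With 120 usable pairs (an assumed 20% loss): 1.0986 ± 0.1812, giving 0.72 to 0.86.

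**Precision of sensitivity for LVEF below 50%.** Wilson 95% intervals for an observed sensitivity of about 90%:

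- One third affected: 150 × 1/3 = 50 cases; 45/50 gives 79% to 96%.
- 20% affected (assumed): 30 cases; 27/30 gives 74% to 97%.
- 10% affected (assumed): 15 cases; 14/15 gives 70% to 99%.

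The one-third figure is for heart failure in routine attenders and may not carry over. Section 6.3 excludes "Patients with any previous measurement of LVEF <50"% and known heart failure, which would lower it. Section 6.2 requires a pacing burden of at least 20%, which could raise it.

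**Does the sentence enter any of this?** The intervals depend on the number of usable pairs, the number of cases and the observed results. Keeping, deleting or rewording the power sentence leaves all of them unchanged.

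**The case for a change.** The best case for a change is that this is no mere omission that an analysis plan could fill. The protocol makes an affirmative claim straight after text that takes away its basis, and correcting it would cost one sentence. Against a zero null, a correlation of 0.50 or more is almost certain to be significant, so the claim could lend weight to a result that says little about agreement. It also gives no hint that sensitivity rests on far fewer than 150 people.

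Part of this stands. The remark is unsupported: it has no hypothesis, error rate or source, and no title in the reference list concerns AI-derived LVEF. Sensitivity will indeed be less precise than the correlation.

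The rest is weaker. The protocol disclaims a formal calculation and then voices an expectation; that is loose, but not a strict contradiction. The feared misreading needs a significance test of the correlation, and sections 11.1 and 11.2 plan none. Whether a correlation can show similar accuracy is a separate question about the choice of primary measure, and rewording section 11.1 would not settle it. Stating a null, target, error rate and source would add detail that an exploratory pilot does not need.

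**Conclusion.** No change to the plan follows. The sentence in section 11.1 is unsupported and undefined, but it is not shown to be wrong: it claims no figure, and under assumed hypotheses power at 150 runs from about 33% to nearly 100%. A pilot needs no formal power calculation, and the protocol says plainly that none was done and that all analyses are exploratory. Following the plan as written gives the same sample, correlation, accuracy measures and intervals as a reworded version would.

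A reader who wants to judge 150 can use precision: about 0.73 to 0.85 for a correlation of 0.80 with all pairs usable, and 79% to 96% for a sensitivity of 90% with 50 cases, widening with fewer. These figures rest on assumed correlations, an assumed sensitivity and an uncertain share with LVEF below 50%. The conclusion does not depend on them. It rests on the absence of any planned test or decision that uses the power remark.
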